## 2.4.9 Analyses of proprotein convertase subtilisin kexin type 9 levels

PCSK9 levels (total and free), percent change from baseline at each time point for each treatment group will be provided. All measurements, scheduled or unscheduled will be assigned to analysis windows (see Section 2.4.4 on which value to select) in order to provide an assessment for these time points. The time profile of mean PCSK9 levels will be plotted by treatment group with the corresponding SEs.

Analyses of PCSK9 will be performed overall and by randomization stratum as per IVRS (for strata with at least 10% of patients) and may be replicated in the subgroup of patients in the region North America.

#### 2.5 DATA HANDLING CONVENTIONS

#### 2.5.1 General conventions

The following formulas will be used for computation of parameters.

#### Time since/duration of event

Time since/duration of [event] (years) = (Date of informed consent – Date of [event]\*) / 365.25.

[event] can be diagnoses, quit smoking, menopause, ...

\*: In case the month of event would be missing, it will be put equal to JANUARY if the year of event equals the year of informed consent; it will be put equal to JULY otherwise. In case only the day of event would be missing, it will be put equal to 1.

#### Date of last dose of alirocumab

The date of the last injection is equal to the last date of administration reported on injection administration e-CRF page, or missing if the last administration date is unknown.

#### Date of last usual treatment care

Property of the Sanofi Group - strictly confidential

The date of the last usual treatment care is equal to the last date of usual care reported on usual care medication for LMT e-CRF page, or missing if the last medication date is unknown.

#### HbA1c formula

The master equation for converting National Glycohemoglobin Standardization Program (NGSP) units into International Federation of Clinical Chemistry (IFCC) units (8) is:

 $HbA1c \, mmol/mol = 10.93 \, x \, HbA1c \, \% - 23.5$ 

## Renal function formulas

Estimated GFR value will be derived using the Modification of Diet in Renal Disease (MDRD) equation:

 $186.3 \times (\text{serum creatinine in } \mu \text{mol/L} / 88.4)^{-1.154} \times (\text{age in years})^{-0.203} (\text{x } 0.742 \text{ if female, x } 1.21 \text{ if race is "Black or African American"})$ 

## Lipids variables and laboratory safety variables

For data below the lower limit of quantification (LLOQ)/limit of linearity, half of the lower limit value (i.e., LLOQ/2) will be used for quantitative analyses. For data above the upper limit of quantification (ULOQ)/limit of linearity, the upper limit value (i.e., ULOQ) will be used for quantitative analyses.

## 2.5.2 Missing data

For categorical variables, patients with missing data are not included in calculations of percentages unless otherwise specified. When relevant, the number of patients with missing data is presented.

# Handling of computation of treatment duration if open-label alirocumab/usual care treatment first or end of treatment date is missing

If the first or last administration of open-label alirocumab/usual care treatment date is missing, the exposure duration and compliance will be left as missing.

# Handling of safety and efficacy analysis periods and survival analysis if investigational medicinal product end of treatment date is missing

If the last date of administration of open-label alirocumab/usual care treatment is missing, then this date is imputed to the earliest between:

- The last day of the month and year, when applicable or else the 31st of December of the year;
- The date of the end of treatment visit (Week 24 visit for completer, early end of treatment visit for patients who prematurely discontinued the IMP);
- And the date of the last contact;

for the purpose of safety and efficacy analysis period start and/or end.

## Handling of medication missing/partial dates

No imputation of medication start/end dates or times will be performed. If a medication date or time is missing or partially missing and it cannot be determined whether it was taken prior or concomitantly, it will be considered a prior, concomitant, and post-treatment medication.

## Handling of adverse events with missing or partial date/time of onset, worsening, seriousness

Missing or partial AE onset dates/times will be imputed so that if the partial AE onset date/time information does not indicate that the AE started prior to treatment or after the TEAE period, the AE will be classified as treatment-emergent. These data imputations are for categorization purpose only and will not be used in listings. No imputation is planned for date/time of AE resolution.

# Handling of adverse events when date and time of first investigational medicinal product administration is missing

When the date and time of the first open-label alirocumab/usual care treatment administration is missing, all AEs that occurred on or after the day of randomization will be considered as TEAEs.

When the time of the first open-label alirocumab/usual care treatment administration is missing, all AEs that occurred on the day of the first open-label alirocumab/usual care treatment administration will be considered as TEAEs.

# Handling of missing assessment of relationship of adverse events to investigational medicinal product

If the assessment of the relationship to open-label alirocumab/usual care treatment is missing, then the relationship to open-label alirocumab/usual care treatment has to be assumed as possibly related in the frequency tables, but no imputation should be done at the data level.

#### Handling of potentially clinically significant abnormalities

If a patient has a missing baseline, he/she will be grouped in the category "normal/missing at baseline."

For PCSAs with two conditions:

- The first one based on a change from baseline value
- The other one based on a threshold value or a normal range.

If the first condition is missing, PCSA will be based only on the second condition.

For a PCSA defined on a threshold value and/or a normal range, it will be derived using this threshold if the normal range is missing; e.g., for eosinophils the PCSA is >0.5 GIGA/L or >ULN if ULN  $\ge 0.5$  GIGA/L. When ULN is missing, the value 0.5 GIGA/L should be used.

Property of the Sanofi Group - strictly confidential

Measurements flagged as invalid by the laboratory will not be summarized or taken into account in the computation of PCSA values.

#### 2.5.3 Windows for time points

Data analyzed by time point (including efficacy data, laboratory safety data, vital signs, PCSK9, diabetes-related parameters, ADA) will be summarized using the analysis windows given in Table 2 - Analysis windows definition. These analysis windows will be applicable for all analyses, and they are defined to provide more homogeneous data for time point-specific analyses.

**Table 2 - Analysis windows definition** 

Time point	Targeted study day	Analysis window in study days
Week 4	29	15 to 42
Week 8	57	43 to 70
Week 12	85	71 to 98 for usual care
		71 to minimum (98; study day corresponding to the first injection with
		IMP from kit allocated at up-titration IVRS contact) for alirocumab
		group
Week 20	141	127 to 154
Week 24	169	155 to 182
Week 32	225	211 to 238

Study day is calculated from the day of randomization. Day 1 is the day of randomization.

If multiple valid values of a variable exist within an analysis window, the nearest from the targeted study day will be selected. If the difference is a tie, the value after the targeted study day will be used. If multiple valid values of a variable exist within a same day, then the first value of the day will be selected when time is available, else the scheduled visit will be selected.

#### 2.5.4 Unscheduled visits

For efficacy, safety laboratory data, or vital signs, unscheduled visit measurements may be used to provide a measurement for a time point, a baseline, a last or a worst value, if appropriate according to their definitions. The measurements may also be used to determine abnormal/PCSA.

## 2.5.5 Pooling of centers for statistical analyses

Not applicable.

## 2.5.6 Statistical technical issues

Not applicable.

26-Apr-2017

## 3 INTERIM ANALYSIS

No formal interim analysis for efficacy is planned since analysis of primary and key secondary efficacy endpoints will be final at the time of first-step analysis described below.

All efficacy data will be available for final analysis at a cut-off date corresponding to the Week 24 visit of the last patient and both the efficacy and safety analyses will be performed in a first-step analysis. Since safety data are being collected until the end of the study (Week 32), an update of the safety analysis will be performed at the end of the study. If analyses are not needed at Week 24, then they will be included in a second-step analysis at the end of the study.

The first-step analysis will be conducted as soon as all patients have been randomized and have at least all their data up to Week 24 collected and validated, and will consist of a final analysis of the primary and secondary efficacy endpoints up to Week 24, as well as safety analysis performed on all safety data collected and validated up to the common cut-off date, defined as the date of the last Week 24 visit.

The second-step analysis will be conducted at the end of the study and will consist in the updated analysis of safety endpoints until Week 32.

No multiplicity adjustment for multiple analyses is needed because all efficacy analyses will be completed at the time of the first-step analysis.

Analyses methods and conventions described in the other sections of this SAP will be applied for all analyses as applicable. The following additional rules will apply for analyses performed at first step analysis:

- Any lipid assessments within analysis windows up to Week 24 will be taken into account (may include few unscheduled lipid data soon after the cut-off date).
- Patients without end of treatment visit performed at the time of the cut-off date will be considered as ongoing and exposed up to the cut-off date. Therefore:
  - Patients who did not complete treatment period nor prematurely discontinued the study treatment at cut-off date will be analyzed as "ongoing" in the disposition summary;
  - Their TEAE period, treatment period and on-study observation period will end at the cut-off date;
  - Their treatment duration will be derived by considering date of cut-off as last IMP/usual care date.
- AEs occurring, worsening or becoming serious after the cut-off date will not be included in the analyses. However, any available outcome before database lock, regardless of timing in relation to the cut-off date, of an AE starting prior to the cut-off date will be taken into account. Medications, treatment discontinuations/completions, and deaths occurring after the cut-off date will not be included in the analyses.

26-Apr-2017

- 26-Apr-2017 Version number: Final
- Post-treatment period, post-study period are not applicable for ongoing patients. Analyses of post-treatment AEs, post-study deaths, and post-treatment medications will be performed for patients who either completed or prematurely discontinued the treatment before or at the cut-off date.
- Analysis of status at last study contact and proportion of patients with insufficient followup will be provided for patients who either completed or prematurely discontinued the treatment before or at the cut-off date.

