Reasons for treatment discontinuation will be supplied in tables giving numbers and percentages by treatment group. A listing of patients who prematurely discontinued study treatment with further reason provided in free text will be provided.

The incidence of premature treatment discontinuation (irrespective of the reason) and premature treatment discontinuation due to AEs will be presented graphically by treatment group on randomized and treated patients (as treated), using Kaplan-Meier method.

The incidence of premature study discontinuation (irrespective of the reason) and premature study discontinuation due to AEs will be presented graphically by treatment group on randomized and treated patients (as treated), using Kaplan-Meier method.

Patients with insufficient post-treatment follow-up will be described on the safety population by treatment group. Number and percentage of patients with insufficient follow-up, quantitative (in weeks) and qualitative ( $<1, \ge 1$  to  $<3, \ge 3$  to  $<5, \ge 5$  to  $<7, \ge 7$  to <9 weeks) duration of follow-up will be presented by treatment arm. A patient is considered with insufficient post-treatment follow-up in the case of his/her last post-treatment phone-call is:

- For patients receiving alirocumab: less than 9 weeks after the last open-label alirocumab injection, unless patient died before
- For patients receiving another LMT in the usual care arm:
  - o less than 9 weeks after the last dose of usual care treatment or
  - o before Week 31,

26-Apr-2017

whichever comes first, unless patient died before

- For patients randomized to usual care without LMT:
  - o less than 9 weeks after the last on site study visit or
  - before Week 31,
     whichever comes first, unless patient died before.

All major deviations potentially impacting efficacy analyses, randomization, and drug-dispensing irregularities, and other major or critical deviations will be summarized in tables giving numbers and percentages of deviations by treatment group. Patients excluded from the ITT population will be listed as well as patients with major deviation potentially impacting efficacy analyses not resulting in exclusion from ITT population. These deviations are listed in the data review and surveillance plan.

Additionally, the following analysis populations will be summarized by treatment group:

- Randomized population;
- Efficacy population: ITT population;
- Safety population;
- PCSK9 population;
- ADA population.

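### At the first-step analysis, the insufficient-follow-up proportion counts on-schedule completers whose post-treatment call is not yet due

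*SAP*

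**What the plan says.** SAP 2.2 (Disposition of Patients) introduces the measure: "Patients with insufficient post-treatment follow-up will be described on the safety population by treatment group". A patient is classed by the date of the last post-treatment phone call. Follow-up is insufficient in these cases:

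- Alirocumab: the call is "less than 9 weeks after the last open-label alirocumab injection, unless patient died before".
- Usual care with an added lipid therapy: the call is "less than 9 weeks after the last dose of usual care treatment or" before Week 31, taking the earlier limit.
- Usual care with no added therapy: the call is "less than 9 weeks after the last on site study visit or" before Week 31, again taking the earlier limit.

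Death is the only exemption in all three. Nothing covers a call that is not yet due.

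SAP Section 3 (Interim Analysis) limits first-step safety data to a "common cut-off date, defined as the date of the last Week 24 visit". For this measure it says that the "proportion of patients with insufficient followup will be provided for patients who either completed or prematurely discontinued the treatment" no later than that cut-off. The patients left out are those Section 3 calls ongoing, who have had no end-of-treatment visit by the cut-off.

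The protocol supplies the timing. The last planned injection is at Week 22, the end-of-treatment visit is at Week 24, and the post-treatment phone contact is at Week 32, Day 225 ±7 (Section 1.2). Section 10.3.4 adds a final call 10 weeks after premature discontinuation for patients who stop treatment and will not resume the schedule. SAP Section 4 places the Week 24 database lock 40 days after the last Week 24 visit.

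**The concern.** Section 3 recognises that post-treatment follow-up is immature at the first step, but it filters on the wrong condition. It asks whether treatment has ended, when what matters is whether the call is due. With the cut-off at the last patient's Week 24 visit, almost everyone has completed or stopped treatment, so the filter removes almost nobody. Patients who completed shortly before the cut-off stay in the denominator without a qualifying call, because none was possible yet.

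The table exists to show how much post-treatment safety follow-up was lost. At the first step it would mix real losses with patients followed exactly as planned. Protocol 6.3 and 11.5 foresee the first step for scientific communication, so the figure could be read before the Week 32 data exist.

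**Working it through.** **Inputs.** Visit days are from protocol 1.2, the 9-week and Week 31 limits from SAP 2.2, the cut-off from SAP Section 3, the 40-day lock from SAP Section 4, and N = 420 from SAP 1.1. The recruitment period is not in the documents. I assume uniform accrual over R = 26, 52 or 78 weeks.

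**Step 1: reproduce the plan's timing.** Study day = 7 × week + 1. Week 22 is Day 155, Week 24 is Day 169, Week 31 is Day 218 and Week 32 is Day 225. Then 225 − 155 = 70 days = 10 weeks, which agrees with protocol 10.1.2.5, where the Week 32 call is placed 10 weeks after the last injection.

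**Step 2: earliest qualifying call for a patient on schedule.**

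- Alirocumab: 155 + 63 = Day 218.
- Usual care, last dose or on-site visit at Week 24: the earlier of 169 + 63 = Day 232 and Week 31 = Day 218, so Day 218.

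Both arms share Day 218, which is also the first day of the Week 32 call window.

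**Step 3: who cannot qualify by the cut-off.** Day 218 is 218 − 169 = 49 days after the Week 24 visit. The target call day is 225 − 169 = 56 days after it. A completer whose Week 24 visit fell within the last 49 days before the cut-off cannot have a qualifying call. If calls are made on the target day, the interval is 56 days.

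**Step 4: share of patients.** Under uniform accrual, share = g / (7R), where g is the interval in days. If data stop at the cut-off, g = 49 to 56. If calls up to the lock count, g = 49 − 40 = 9 to 56 − 40 = 16.

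| R (weeks) | Data stop at cut-off | Calls up to lock count |
|---|---|---|
| 26 | 49/182 to 56/182 = 27-31% (113-129 of 420) | 9/182 to 16/182 = 5-9% (21-37) |
| 52 | 49/364 to 56/364 = 13-15% (57-65) | 9/364 to 16/364 = 2.5-4.4% (10-18) |
| 78 | 49/546 to 56/546 = 9-10% (38-43) | 9/546 to 16/546 = 2-3% (7-12) |

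**Step 5: effect on the table.** Let f be the not-yet-due share and p the true insufficient share among the rest. The table shows f + (1 − f)p. With an assumed p of 5% and R = 52:

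- Data stop at cut-off: 0.135 + 0.865 × 0.05 = 17.8%, and 0.154 + 0.846 × 0.05 = 19.6%. The table would show about 18-20%.
- Calls up to lock count: about 7.3% to 9.2%.

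**Step 6: effect on an arm comparison.** If f is the same in both arms, the reported difference is (1 − f) times the true one. At R = 52 with data stopping at the cut-off, that is about 85-87% of it.

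**The case against.** The strongest reply is that this is one provisional, descriptive table. Under the protocol the first step is done only if needed. Safety is updated at the end of the study, when every call is due. SAP 2.2 also tabulates study completion, study discontinuation with reasons and status at last contact, and gives Kaplan-Meier curves for study discontinuation. That largely stands and is why the point is minor. One part is inferred: the second step promises an update of safety endpoints, whereas this measure sits under disposition, so a re-run is likely but not stated.

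Two gaps in the text could shrink the effect. SAP 2.2 does not say how to class a patient who has had no post-treatment call. Insufficient is the natural reading, but treating such patients as missing would reduce the inflation. Section 3 lists what is excluded after the cut-off (adverse events, medications, treatment discontinuations and completions, deaths) without naming phone calls. Its general limit on first-step safety data points to the larger figures, but the lock-based figures cannot be ruled out.

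Three stronger readings are tempting and do not hold:

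- A reader might infer that every completer is reported as insufficient. Section 3 only defines who is analysed; a completer with a call on or after Day 218 is not flagged.
- A reader might infer that the table would mostly count on-schedule patients. That needs a true loss rate, which the documents do not give. At the assumed 5% and 52 weeks, the on-schedule share of those flagged is about three quarters if data stop at the cut-off (13.5/17.8), but about a third to a half if calls up to lock count (2.5/7.3 to 4.4/9.2).
- A reader might infer that a difference between arms cannot be read. Patients are centrally randomised and both arms share Day 218 when on schedule, so similar inflation is expected in each. A real difference is diluted, not hidden or created.

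**Conclusion.** The point holds, as a minor one. On the natural reading of SAP 2.2, following Section 3 as written counts on-schedule completers as insufficient when their Week 24 visit fell within about 49 to 56 days before the cut-off. The first-step proportion is then too high in both arms, to a similar degree.

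The mechanism rests only on stated rules and the visit schedule, plus the reading that a patient with no call yet is insufficient. The size is much less certain. It depends on an assumed recruitment period with uniform accrual, and on whether calls between cut-off and lock count. Across 26 to 78 weeks of recruitment it runs from about 2% to 31%, and on this reading it is above zero in every case examined. Efficacy results, type I error and the TEAE analyses do not depend on it.

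**What to change.** In SAP Section 3, limit the first-step summary to patients whose follow-up threshold has been reached by the data cut. For alirocumab that is 9 weeks after the last injection. For usual care it is the earlier of Week 31 and 9 weeks after the last dose (or the last on-site visit where no therapy was added). Alternatively, keep all patients and show follow-up not yet due as its own category.

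Either way, state three things:

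- whether the data cut for calls is the cut-off or the lock;
- how a patient with no post-treatment call is classed;
- that the final proportion is reported at the second-step (Week 32) analysis.

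The cost is a short SAP addition and, with the restriction, a smaller first-step denominator. No visit, data collection or efficacy analysis changes.

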## 4 DATABASE LOCK

The database for Week 24 analysis is planned to be locked at 40 calendar days after last patient last on-site Week 24 visit. The database for Week 32 analysis is planned to be locked at 20 calendar days after last patient last Week 32 phone call.

26-Apr-2017

## 5 SOFTWARE DOCUMENTATION

All summaries and statistical analyses will be generated using SAS version 9.2 or higher.

26-Apr-2017

